8.2. Setting

Clinical practice and treatment of each patient will follow as determined by each treating HCP individually. There will be no interference from Pfizer with the HCP's diagnostic and treatment decisions. The decision to treat a patient with lorlatinib will be prior to and independent of participation in the real world data collection and according to the clinical judgement of their HCP. Therefore, the data collection will in no way influence prescribing patterns or treatment decisions. If eligible, the patient will receive treatment through Pfizer's expanded access program independent of involvement in the collection of real world data.

HCPs treating a patient approved to receive lorlatinib via Pfizer's expanded access program will be invited to take part in the real world data collection. Upon HCP agreement, they will receive access to the EDC, where they can enter data into the DCT.

The first pediatric neuroblastoma patient received lorlatinib in March 2017 as part of expanded access programs and the program is ongoing. Data collection is anticipated to initiate in January 2021 and is estimated to have last patient entered into real world dataset at

PFIZER CONFIDENTIAL

the end in December 2023. Database lock would occur in February 2024, as outlined in [Section 5](#).

Data will be collected via DCT at multiple time points for patients who are receiving ongoing treatment. These timepoints will be determined by HCP standard practice for treatment and follow-up of their patients. Visits are anticipated to occur every 3-4 months, corresponding with re-supply of lorlatinib. Data will be collected on a continual basis until discontinuation of treatment with lorlatinib, death, loss to follow-up or end of study, whichever comes first.

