5. MILESTONES

Milestone	Planned date
Start of data collection	25 February 2021
Treatment completed population – data collection completion date	25 March 2021
Progress report – Treatment completed population	28 April 2021
Interim report 1 – Year 1	31 December 2021
Interim report 2 – Year 2	31 December 2022
End of data collection (Last patient added to real world data collection)	31 December 2023
Database lock	15 February 2024
Final study report	31 March 2024

[figure not shown]

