Current treatment approach for high-risk patients include induction chemotherapy (reduce tumor burden by shrinking tumor), local control (delayed surgery to remove tumor), consolidation (myeloablative therapy with stem cell rescue performed in tandem) and maintenance therapy (GD2-directed therapy, which is painful and toxic).¹¹ A published meta-analysis of three European SIOP Neuroblastoma Group (SIOPEN) trials on standard backbone chemotherapy regimens showed poor outcomes in both relapsed and refractory neuroblastoma patients.¹² It is important to note that, unlike childhood leukemias, there is no standard approach for high-risk neuroblastoma patients who suffer a relapse and there is no known curative therapy. Response rates in clinical trials of relapsed/refractory neuroblastoma ranged from 20-64%.¹² After treatment, progression occurred in 54% of patients with refractory disease versus 87% of patients with relapsed disease.¹² Overall median OS was 16.1 months, with longer median OS for patients with refractory disease compared to relapsed disease.¹² Neuroblastoma has significant heterogeneity, therefore risk stratification has become an important factor in identifying novel biomarkers to inform treatment decisions.⁹

Initial reports of anaplastic lymphoma kinase (ALK) gene amplification and overexpression suggested a role of ALK in neuroblastoma.^{13,14} Notably, ALK activating mutations were first discovered in the germline of families where the disease is inherited, and subsequently found to be present in somatic tissue in ~10% of patients at diagnosis.¹⁵⁻¹⁸ The majority of patients with familial neuroblastoma have germline mutations in ALK.¹⁸ Sporadic neuroblastoma tumors also occasionally harbor ALK abnormalities, including 4% of tumors with genomic amplification and approximately 10% with missense mutations.^{14,17-19} Furthermore, the presence of ALK mutation correlates with worse prognosis in high and intermediate risk patients.²⁰ The detection of ALK mutations and/or amplifications in primary neuroblastomas, provides a molecular rational for targeted therapy of neuroblastoma.¹⁶ It has been demonstrated that downregulation of ALK suppressed proliferation of neuroblastoma cells harboring mutated ALK.¹⁵

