8.2.1. Inclusion criteria

Patients must meet all the following inclusion criteria to be eligible for inclusion in the study:

1. Patient treatment with lorlatinib is initiated through Pfizer's expanded access program for treatment of ALK+ neuroblastoma.
2. HCP documentation of at least one tumor assessment of response after patient has had at least one dose of lorlatinib
3. Evidence of a personally signed and dated informed consent document indicating that the patient (or a legally acceptable representative, or a waiver of informed consent has been granted by the IRB/IEC) has been informed of all pertinent aspects of the study.

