8.5. Study size

With primary goal of the Pfizer expanded access program is to provide treatment access to patients with an unmet clinical need, no formal power calculations were conducted to determine sample size. Furthermore, the data collection does not involve hypotheses testing (via statistical testing) and it is primarily being conducted to understand treatment outcomes. Target sample size will comprise every patient fulfilling eligibility criteria above and providing informed consent for real world data collection.

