Partial Response (PR)	PR in at least one component and all other components are either CR, MD (Bone marrow), PR (Soft tissue or Bone) or Not involved (NI); no component with PD.													
Minor Response (MR)	PR or CR in at least one component but at least one other component with SD; no component with PD.													
Stable Disease (SD)	SD in one component with no better than SD or NI in any other component; no component with PD.													
Progressive Disease (PD)	Any component with PD													
Best Overall response	HCP Reported Response	Derived as the best overall response taking the HCP Reported Response observed up to the data cut-off date for a specific milestone. (The												

PFIZER CONFIDENTIAL

	Repeated using Derived Objective Response	sequence order from best to worst is CR, PR, MR, SD, PD.)
Overall Response Rate (ORR)	Best Overall Response	Derived as Best overall response of CR+PR of the total population observed up to the data cut-off date for a specific milestone.
Duration of response	Treatment Start and HCP Reported Response Date	Derived as (Date of PD or death, whichever occurs first) – (Date of PR or CR, whichever occurs first) + 1
Progression free survival (PFS)	Treatment Start and HCP Reported PD/Death Date	Derived as (Date of PD or death (by any cause in the absence of PD)) – (Treatment start date) + 1
Duration of treatment	Treatment Start and Stop Dates	Derived as (Treatment stop date) – (Treatment start date) + 1
Overall survival (OS)	Treatment Start and Death Dates	Derived as (Date of death) – (Treatment start date) + 1

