8.9. Limitations of the research methods

Patients included in this program represent a convenience sample such that supplemental data will be collected on patients of HCPs who are willing to participate in the data collection component and initiated treatment with lorlatinib through Pfizer's expanded access program.

PFIZER CONFIDENTIAL

All data captured in the DCT will be limited to information available to the HCP participating in the program. Information on health care services received outside the HCP's care setting will be unavailable.

Data will be entered directly by the participating HCP and therefore may be subject to entry errors and resulting inaccuracies in reporting. Although there will be data checks in place to improve internal consistency of the data, responses will not be validated against the patients' medical records by an independent reviewer.

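### Patients treated since March 2017 can enter the dataset only from early 2021, yet OS, PFS and treatment duration run from first dose; if earlier deaths are under-captured OS reads too long, and the plan cannot show whether they are

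*Combined protocol and SAP*

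**What the plan says.** **Timing.** Section 8.2 records that "The first pediatric neuroblastoma patient received lorlatinib in March 2017 as part of expanded access programs and the program is ongoing". The same section says "Data collection is anticipated to initiate in January 2021"; the milestones table in section 5 gives "Start of data collection 25 February 2021".

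**Entry.** Under sections 8.1 and 8.2 the treating HCP must agree to take part. Inclusion criterion 3 in section 8.2.1 asks for "Evidence of a personally signed and dated informed consent document indicating that the patient" or a legally acceptable representative has been informed, and it also accepts an IRB/IEC waiver. Section 9.2 repeats the waiver. Section 8.5 does not: it describes the target as eligible patients "providing informed consent for real world data collection".

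**Who is sought.** Section 8.1 covers patients whose treatment is finished, ongoing or new. Section 8.7.1 gives those who finished before January 2021 the first progress report, and section 5 schedules their data collection to be complete by 25 March 2021.

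**Time origin.** In section 8.7.5, OS is "Derived as (Date of death) – (Treatment start date) + 1". PFS and duration of treatment also start at the treatment start date. The censoring rules in section 8.7.6 say nothing about entry after time zero.

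**Safeguards.** Disposition in section 8.7.3 counts patients on, continuing and stopping treatment. It does not compare the dataset with everyone supplied. Section 8.9 says "Patients included in this program represent a convenience sample", with reference to HCPs' willingness, and does not mention survival.

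**The concern.** A child treated in 2017 can join the dataset almost four years after time zero. A child still attending re-supply visits is in contact with the HCP when consent is sought. For a child who died in 2018, someone must approach the family or obtain a waiver, and section 9.4 leaves IRB/IEC approvals to each HCP. The treatment-completed group, where earlier deaths would be found, has one month of scheduled collection (25 February to 25 March 2021). It is therefore plausible, though not documented, that capture depends on survival.

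If it does, the retained early starters are enriched for long survivors, whose whole time since first dose counts as time at risk. Some of the deaths that belong beside that time are missing. PFS and OS are objective 3, and duration of treatment is part of objective 2. There is no comparator, and the protocol's own background gives a figure that invites comparison: "Overall median OS was 16.1 months" in relapsed or refractory disease.

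**Working it through.** The plan has no power calculation or expected survival figure to reproduce, so this is an illustration for OS only.

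**Inputs from the documents**
- First treatment March 2017 (8.2), taken as 1 March.
- Opening of data collection 25 February 2021 (section 5): 47.9 months later.
- Last patient added 31 December 2023 (section 5), used as the cut-off: 82.0 months after 1 March 2017.
- Median OS 16.1 months (section 6), a historical figure borrowed as the assumed truth.

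**Assumptions not in the documents**
- Exponential survival and uniform treatment starts over the 82.0 months.
- Complete follow-up for death to the cut-off.
- Every patient alive at opening is captured; earlier deaths are captured with probability c.

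**Step 1: how many deaths are exposed to the problem.**
- Share starting before opening: 47.9 / 82.0 = 58.4%.
- λ = ln 2 / 16.1 = 0.04305 per month, so λ × 47.9 = 2.062.
- Share of those dead by opening: 1 − (1 − e^−2.062) / 2.062 = 1 − 0.873 / 2.062 = 57.7%.
- Share of all patients: 0.584 × 0.577 = 33.7%.

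**Step 2: the planned Kaplan-Meier estimate from first dose** (large simulation, true 24-month OS e^(−0.04305 × 24) = 36%).

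| Capture of earlier deaths | Median, months | 24-month OS |
|---|---|---|
| 100% | 16.1 | 36% |
| 75% | 17.3 | 38% |
| 50% | 18.9 | 41% |
| 25% | 21.2 | 45–46% |

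Delayed entry at opening, or restriction to patients starting after opening, returns about 16 months.

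**Step 3: sensitivity to the assumptions** (same model, followed to the database lock of 15 February 2024).

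| Assumed true median and starts | 75% | 50% | 25% | 0% |
|---|---|---|---|---|
| 16.1, starts to December 2023 | 17.3 | 18.8 | 21.0 | 24.2 |
| 16.1, all starts before opening | 18.0 | 21.2 | 26.3 | 34.5 |
| 9, starts to December 2023 | 9.4 | 10.0 | 10.8 | 12.1 |
| 24, starts to December 2023 | 26.1 | 28.9 | 32.3 | 36.6 |

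The shift is upward in every row and vanishes at full capture.

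**Step 4: precision at 50 patients, full capture, December 2023 cut-off.**
- Expected deaths: λ × 82.0 = 3.530, and 50 × [1 − (1 − e^−3.530) / 3.530] = 50 × 0.725 = 36.
- Of these, before opening: 50 × 0.337 = 17. Delayed entry discards them.
- Central 95% of simulated medians: about 10 to 24 months as planned, about 8 to 29 with delayed entry.
- New starters: 50 × (82.0 − 47.9) / 82.0 = 21 patients. With λ × 34.1 = 1.468, expected deaths are 20.8 × [1 − (1 − e^−1.468) / 1.468] = 20.8 × 0.476 = 10.

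**The case against.** **Earlier deaths are eligible.** From section 8.5 alone a reader might infer that consent is the only way in and that children who died before 2021 are shut out. The documents do not support that. Criterion 3 and section 9.2 allow a representative or a waiver, and sections 5, 8.1 and 8.7.1 seek out patients whose treatment has ended. Section 8.7.3 lists death and progression among the reasons for stopping. The design is partly retrospective; it is not left-truncated by rule. This stands, and it makes the point conditional. It shows intent to capture, however, and not completeness.

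**The mechanism and capture rates are assumed.** This also stands. HCP refusal may remove living and dead patients alike, and the limit of 50 in section 8.1 is not shown to bind. That consent dates from 2021 is itself an inference: no consent date is given, but consent must concern this study and precede study-specific activity.

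**The illustration is not the planned OS analysis.** Section 8.2 ends collection at discontinuation of lorlatinib, and section 9.3 treats that date as the last visit, so later deaths may go unrecorded. The medians above are therefore no forecast of what the report will show.

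**The shift is small against noise.** At 50 patients, shifts of 1 to 5 months lie inside the sampling range of about 10 to 24 months. True, but the planned confidence limits describe random error around a shifted value and give no warning of the shift.

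**The analysis is descriptive and a convenience sample is declared.** No comparison with 16.1 months is planned. Still, section 11 foresees reporting to regulators and journals, and the caveat in section 8.9 concerns which HCPs take part, not which of their patients.

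**Delayed entry is costly.** It discards about 17 of 36 deaths, which would be valid data if capture were complete. For treatment duration it would remove the whole treatment-completed cohort. This limits it to a secondary role.

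**Conclusion.** The point holds as a conditional risk. The gap of up to about four years between time zero and possible entry, the count from first dose, the absence of delayed entry, and the lack of any treated-versus-captured count are all in the text. If earlier deaths are under-captured relative to survivors, OS is biased upward. Under the stated assumptions the shift in the median is about 1.2, 2.8 or 5.1 months at 75%, 50% or 25% capture. If capture is complete, the bias is zero. The defect is that the plan gives no means of telling these cases apart.

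A reader might go further and conclude that OS, PFS and treatment duration are all inflated. The documents do not show under-capture, and only OS was modelled; the other two follow to the extent that they correlate with survival. Nor does the direction carry over to treatment duration in the first progress report: that cohort is restricted to patients who have already stopped, which selects the other way.

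**What to change.** 1. **Denominator table.** At each milestone report the number of patients started in the expanded access program and the number captured, by start year. Add status (on drug, stopped, dead) where program records and consent rules permit. Whether those records hold vital status is not stated, so status may be incomplete for children not captured. Cost: one table from program supply records.
2. **Sensitivity analysis.** Keep the planned Kaplan-Meier estimate as the main result. Beside it show OS and PFS restricted to patients starting lorlatinib on or after the opening of data collection, and/or with delayed entry at the inclusion date. For treatment duration use only the new-starter restriction. State that these analyses discard earlier events and are imprecise at 50 patients or fewer. Cost: one or two extra runs, plus collection of the consent or inclusion date, which section 8.3 does not list. Settle whether the opening is January or 25 February 2021, since the restriction depends on it.
3. **Text.** Name survival-dependent capture in section 8.9, and reconcile section 8.5 with the waiver allowed in sections 8.2.1 and 9.2. Cost: two sentences.

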7. RESEARCH QUESTIONS AND OBJECTIVES

The primary goal of the Pfizer expanded access program is to provide access to lorlatinib to patients with a serious or immediately life-threatening disease/condition who have exhausted all other standards of care and are not eligible for a clinical trial. Treatment is delivered by the healthcare professional (HCP) as sponsor of the expanded access request and according to a treatment plan approved institutional review board/independent ethics committee as required by local laws and regulations or institutional requirements.

The overall goal of this real-world data collection is to assess demographic, clinical characteristics and real-world effectiveness of pediatric neuroblastoma patients who initiated treatment with lorlatinib through an expanded access program. Data will be collected to address the following specific objectives:

1. Describe the demographic and clinical characteristics of pediatric neuroblastoma patients who initiated treatment with lorlatinib through an expanded access program
2. Evaluate the effectiveness of treatment with lorlatinib in pediatric neuroblastoma patients in terms of duration of treatment, HCP reported response, and duration of response
3. Estimate progression free survival and overall survival
4. Collection of safety data

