8.3. Variables

Variables will include demographics at the start of lorlatinib treatment (age, gender, race, body surface area (BSA)), clinical characteristics (date of initial diagnosis, high risk at diagnosis, ALK aberration date of sample collection and testing, testing platform, ALK and other genetic mutations, ALK amplification, translocation or over-expression, and MYCN amplification, prior anti-cancer treatment, ALK inhibitor use, disease status), treatment start date, starting dose, resupply date(s), BSA, response assessment (date, disease status, HCP reported response, International Neuroblastoma Response Criteria (INRC) response assessment criteria²⁸ and assessment modality), last date of lorlatinib, patient alive, date of death, date of discontinuation of lorlatinib and reason for discontinuation of lorlatinib. Safety data will be collected in DCT as outlined in [Section 10](#).

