8.7.3 Patient Disposition and Demography

Patient disposition will account for the number of patients receiving treatment, continued treatment and discontinued treatment at a specific milestone. Potential reasons for discontinuing treatment will include disease progression, adverse event excluding death, death, lost to follow up, and other.

Demographic and patient characteristics will include variables as noted in [Section 8.3](#). Additional variables will be statistically derived and reported including time since initial diagnosis. Time since initial diagnosis, in months, will be derived as: $12*((\text{Date of initial diagnosis}) - (\text{First Date of lorlatinib Treatment}) + 1) / 365.25$.

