8.7.6 Statistical summaries

Demographic and clinical characteristics

The number and percentage of patients will be presented within each categorized variable. In addition, descriptive statistics for continuous variables will include the mean, standard deviation, median, interquartile range, minimum and maximum.

The demographics will also be presented by subgroups for any subgroups with more than 5 patients.

HCP's reported objective response

For each response component (with the exception of best response), the responses will be listed along with the date of the assessment. A derived objective response will be produced and compared to the HCP overall reported response for confirmation of robustness.

Best Overall Response (BOR) and Overall Response Rate (ORR)

For the BOR, the number and percentage of patients in each ordered category will be presented and summarized by baseline disease status. In addition, the ORR will be presented including the Clopper Pearson 95% Confidence interval.

PFIZER CONFIDENTIAL

Duration of response

The number and percentage of patients will be presented within each of the following categories for duration of response: 0 to <3 months; 3 months to <6 months; 6 months to <1 year; 1 to <2 years; 2 to <3 years >3 years; lost to follow-up. Kaplan-Meier (KM) estimates will be used to give the median, Q1 and Q3 duration of response, with 95% confidence limits. If a patient does not show symptoms of progressive disease, their duration of response will be censored at their last visit date prior to the data cut-off date.

Time to event

KM estimates will be presented, where possible, for duration of treatment, progression free survival and overall survival (i.e., time to death). The following censoring rules will be applied:

- Duration of treatment

Patients who have not discontinued treatment at the data cut-off date will be censored based on the last recorded date when the patient was known to be continuing treatment prior to the data cut-off date.

- Progression free survival

Patients who have not experienced PD or died at the data cut-off date will be censored at the date of last contact prior to the data cut-off date.

- Overall survival

[figure not shown]
Any patient not known to have died at the data cut-off date will be censored based on the last recorded date on which the patient was known to be alive prior to the data cut-off date.

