9.3. Patient withdrawal

Patients may withdraw from the study at any time at their own request, or they may be withdrawn at any time at the discretion of the HCP or sponsor for safety, behavioral, or administrative reasons. In any circumstance, every effort should be made to document patient outcome, if applicable. The HCP would inquire about the reason for withdrawal and follow-up with the patient regarding any unresolved adverse events.

PFIZER CONFIDENTIAL

If the patient withdraws from the data collection, and also withdraws consent for disclosure of future information, no further evaluations should be performed, and no additional data should be collected. The sponsor may retain and continue to use any data collected before such withdrawal of consent.

Treatment discontinuation or loss to follow-up do not constitute patient withdrawal, date of discontinuation or loss to follow-up will be considered last visit date for that patient.

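### Overall survival runs to death, but Section 8.2 ends routine collection at lorlatinib discontinuation and no later alive dates are planned, so the OS estimate can be biased in either direction

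*Combined protocol and SAP*

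**What the plan says.** - **Collection.** Section 8.2: "Data will be collected on a continual basis until discontinuation of treatment with lorlatinib, death, loss to follow-up or end of study", with the first of these to occur applying. Visits are expected every 3-4 months, in step with drug re-supply.
- **Last visit.** Section 9.3 says of patients who stop treatment or are lost that the "date of discontinuation or loss to follow-up will be considered last visit date for that patient".
- **Objective and endpoint.** Section 7 sets the objective "Estimate progression free survival and overall survival". Section 8.7.5 builds OS from "Treatment Start and Death Dates", with no limit to time on treatment. Progression-free survival (PFS) and duration of response (DOR) likewise run to progressive disease (PD) or death.
- **Censoring (8.7.6).** For OS, a patient not known to have died "will be censored based on the last recorded date on which the patient was known to be alive". For PFS: "Patients who have not experienced PD or died at the data cut-off date will be censored at the date of last contact". DOR alone is censored at the last visit date.
- **Fields (8.3).** The tool includes "last date of lorlatinib, patient alive, date of death, date of discontinuation of lorlatinib and reason for discontinuation of lorlatinib". No date last known alive is listed.
- **Safety route (Section 10).** All serious adverse events go on the tool, and a fatal malignancy during the study or the safety reporting period must be recorded as one. That period runs to the end of an observation period that is not defined, and covers at least 28 days after the last dose.
- **Reasons for stopping (8.7.3).** "Potential reasons for discontinuing treatment will include disease progression, adverse event excluding death, death, lost to follow up, and other".

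**The concern.** An endpoint that continues after treatment needs data from after treatment. For a patient who stops alive, the plan does not say whether the vital-status fields stay open, until when, or for whom they are updated. If Section 8.2 is followed as written, such a patient is last known alive at or shortly after stopping. Since progression is a listed reason for stopping, that censoring is plausibly related to prognosis, which Kaplan-Meier estimation assumes it is not.

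Follow-up may also differ within one curve. Sections 8.1 and 8.7.1 bring in patients who had finished treatment before January 2021. Their charts may already show what happened later, whereas prospective patients may be followed only to discontinuation.

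The OS rule in 8.7.6 is sound; what is missing is a plan for the data that feed it. The work is descriptive, so the risk is a misread survival estimate, not a wrong test. It still matters, because Section 11 foresees use with regulators and a manuscript. Section 8.9 says that data are limited to what the treating professional has, but not that collection ends at discontinuation.

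**Working it through.** The plan states no event count or survival assumption, so there is no figure to reproduce. The check below shows direction and possible size under assumed inputs.

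**Inputs from the documents:** up to 50 patients (8.1); first treatment March 2017 (8.2); last entry December 2023 and database lock 15 February 2024 (Section 5); 28-day minimum safety window (Section 10). Median OS of 16.1 months is the Section 6 background figure from other trials, used only to set the scale.

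**Assumptions:** exponential times; uniform starts from March 2017 to December 2023; cut-off at database lock; median time to end of treatment 4, 6 or 9 months; 5-30% of treatment ends being deaths. Eight combinations are kept, with a death hazard 1.4 to 7.6 times higher after stopping than on treatment.

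**Formulas.** With median time to end of treatment m and death share p: a = ln2/m, on-treatment death hazard d = p·a, hazard of stopping alive s = (1-p)·a. The hazard after stopping, q, solves S(16.1) = 0.5, where

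S(t) = exp(-at) + s·[exp(-qt) - exp(-at)]/(a-q).

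If follow-up ends w = 28/30.4375 = 0.92 months after stopping, the hazard that Kaplan-Meier sees beyond time w is

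h = (d + q·s·K)/(1 + s·K), with K = [exp((a-q)w) - 1]/(a-q).

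**Worked case (m = 6, p = 0.20).** a = 0.1155, d = 0.0231, s = 0.0924, q = 0.0692, so q/d = 3.0.
- True S(24) = 0.0625 + 0.0924 × (0.1900 - 0.0625)/0.0463 = 0.317.
- K = 0.940, so h = (0.0231 + 0.0692 × 0.0924 × 0.940)/(1 + 0.0924 × 0.940) = 0.0268.
- Apparent S(24) is about exp(-24 × 0.0268) = 0.526, or 0.527 allowing for the slightly lower hazard in the first 28 days. Bias: +21 points.

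**24-month OS, all eight cases.** The last two columns are simulated. There, all deaths to cut-off are recorded and survivors are censored 28 days after stopping.

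| m | p | q/d | True | 28-day window | Bias (points) | All deaths, no later alive dates | Bias (points) |
|---|---|---|---|---|---|---|---|
| 4 | 5% | 7.6 | 0.309 | 0.676 | +37 | 0.244 | -7 |
| 4 | 10% | 3.5 | 0.319 | 0.578 | +26 | 0.249 | -7 |
| 4 | 20% | 1.4 | 0.343 | 0.418 | +8 | 0.260 | -8 |
| 6 | 10% | 7.1 | 0.301 | 0.654 | +35 | 0.262 | -4 |
| 6 | 20% | 3.0 | 0.317 | 0.527 | +21 | 0.271 | -5 |
| 6 | 30% | 1.6 | 0.337 | 0.421 | +8 | 0.282 | -6 |
| 9 | 20% | 7.6 | 0.306 | 0.609 | +30 | 0.290 | -2 |
| 9 | 30% | 4.3 | 0.315 | 0.528 | +21 | 0.297 | -2 |

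- The middle of the 28-day column is about +24 points. Of about 38-39 deaths per 50 patients, 5-16 are seen; at 24 months about 1-6 patients are at risk instead of 11-12.
- In the right-hand scenario no death is lost. The bias is downward because survivors leave the risk set early while deaths stay in.
- If later deaths are known only for patients who finished before January 2021, and living ones among them are left near stopping, the bias runs from -13 to +9 points.
- If the hazard falls after stopping (m = 4, p = 30%, ratio 0.7), the 28-day window gives 0.299 against a true 0.372, about 7 points too low.
- With full follow-up of 50 patients, the standard deviation of the 24-month estimate is 0.071-0.074; times 1.96, about 14 points either way.

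**PFS and DOR.** Only patients who stop without documented PD are affected. In a rough simulation (median PD 4-9 months, 10-30% stopping before PD, PD hazard 1-2 times higher afterwards), censoring at stopping overstates 12-month PFS by 0 to 5.5 points. I have not repeated that run, and DOR was not calculated.

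**The case against.** The strongest reply is that the documents do not shut out later information. The Section 8.2 sentence closes a paragraph about patients still on treatment. Vital status and death date are separate fields from discontinuation. Patients who have already finished are entered from their records. Section 10 sends fatal malignancy during the study onto the tool, over a period whose end is undefined and for which 28 days is only a minimum.

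Much of this stands. A reader might infer that no death after stopping would be seen and that OS must therefore be overstated. The documents do not support that: they give a route for later deaths, and if all of them arrive the bias is downward and no deaths are lost. Nor can the 28-day results be taken as the expected case; they are the most restrictive reading, and every input except the borrowed median is assumed.

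The reply does not close the gap. A field is not a follow-up schedule, and visits tied to re-supply end with treatment. The instruction in 9.3 to document outcome concerns withdrawal, which that section says discontinuation is not. The safety route seeks deaths but no matching alive dates, so deaths and survivors may be captured unequally.

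**Conclusion.** The point holds for OS. Routine collection ends at discontinuation, no update of alive dates is planned after it, and the endpoint is defined to death. Confidence is high that such updates are not specified, moderate that the resulting censoring would be informative, and low on direction and size, which depend on recording practice.

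Under the stated assumptions, 24-month OS is about 8 to 37 points too high with a 28-day window only (an upper bound; mid-range about 24). It is about 2 to 8 points too low if all deaths but no later alive dates are recorded. The second range lies within sampling error of about 14 points either way, but it is systematic and avoidable.

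A reader might also put PFS and DOR on the same footing. The text does not support that: where PD is recorded at or before stopping, those endpoints are complete. They are a secondary point. The matter should be fixed, but it does not undermine the study.

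**What to change.** 1. **Section 8.2.** State that treatment data are collected to discontinuation and safety data through the Section 10 period. State that vital status and date last known alive are collected from routine-care records until death, loss to follow-up, withdrawal of consent or end of study. Apply this to all patients, including those off treatment at entry, and update deaths and survivors alike before each data cut. Add one date field to the tool.
2. **Section 8.7.6.** Keep the OS rule. Censor DOR and PFS at the last tumor assessment without PD, and state that the last-visit sentence in 9.3 does not set the DOR censoring date. The PFS change is needed because the new vital-status contacts would otherwise extend progression-free time: in the same rough simulation, keeping last contact overstated 12-month PFS by 1.6 to 17.9 points. If PD after discontinuation is also collected, record the start of any later anti-cancer therapy and report how it is handled; 8.3 lists prior treatment only.
3. **Reporting.** Give the number censored within 28 days of discontinuation, separately for patients who finished before January 2021 and the rest.
4. **Fallback.** If post-treatment status cannot be obtained, label OS as having follow-up to discontinuation plus the reporting period, and say so in Section 8.9.

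**Cost:** a protocol amendment with ethics approval (9.4), possibly consent wording (9.2), one added date field, and a brief status update by sites before each data cut. No new visits or procedures are required.
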